15.3 Survey: Examples of potential scenarios for the DCE

a) Variable ATT – High thrombotic risk – High bleeding risk – ECOG-PS Grade ≥ 3

Attributes	Scenario 1	Scenario 2	Scenario 3
ECOG-PS	Grade ≥ 3	Grade ≥ 3	Grade ≥ 3
Thrombotic risk	High	High	High
Bleeding risk	High	High	High
Antithrombotic medication	DOAC or VKA	LMWH (therapeutic)	Antiplatelet agent

b) Variable ATT – high thrombotic risk – low bleeding risk – ECOG-PS Grade ≥ 3

Attributes	Scenario 1	Scenario 2	Scenario 3
ECOG-PS	Grade ≥ 3	Grade ≥ 3	Grade ≥ 3
Thrombotic risk	High	High	High
Bleeding risk	Low	Low	Low
Antithrombotic medication	DOAC or VKA	LMWH (therapeutic)	Antiplatelet agent

c) Variable ATT – low thrombotic risk – high bleeding risk – ECOG-PS Grade ≥ 3

Attributes	Scenario 1	Scenario 2	Scenario 3
ECOG-PS	Grade ≥ 3	Grade ≥ 3	Grade ≥ 3
Thrombotic risk	Low	Low	Low
Bleeding risk	High	High	High
Antithrombotic medication	DOAC or VKA	LMWH (therapeutic)	Antiplatelet agent

d) Variable ATT – low thrombotic risk – low bleeding risk – ECOG-PS Grade ≥ 3

Attributes	Scenario 1	Scenario 2	Scenario 3
ECOG-PS	Grade ≥ 3	Grade ≥ 3	Grade ≥ 3
Thrombotic risk	Low	Low	Low
Bleeding risk	Low	Low	Low
Antithrombotic medication	DOAC or VKA	LMWH (therapeutic)	Antiplatelet agent

e) Variable ATT – high thrombotic risk – high bleeding risk – ECOG-PS Grade 0-2

Attributes	Scenario 1	Scenario 2	Scenario 3
ECOG-PS	Grade 0-2	Grade 0-2	Grade 0-2
Thrombotic risk	High	High	High
Bleeding risk	High	High	High
Antithrombotic medication	DOAC or VKA	LMWH (therapeutic)	Antiplatelet agent

f) Variable ATT – high thrombotic risk – low bleeding risk – ECOG-PS Grade 0-2

Attributes	Scenario 1	Scenario 2	Scenario 3
ECOG-PS	Grade 0-2	Grade 0-2	Grade 0-2
Thrombotic risk	High	High	High
Bleeding risk	Low	Low	Low
Antithrombotic medication	DOAC or VKA	LMWH (therapeutic)	Antiplatelet agent

g) Variable ATT – low thrombotic risk – high bleeding risk – ECOG-PS Grade 0-2

Attributes	Scenario 1	Scenario 2	Scenario 3
ECOG-PS	Grade 0-2	Grade 0-2	Grade 0-2
Thrombotic risk	Low	Low	Low
Bleeding risk	High	High	High
Antithrombotic medication	DOAC or VKA	LMWH (therapeutic)	Antiplatelet agent

h) Variable ATT – low thrombotic risk – low bleeding risk – ECOG-PS Grade 0-2

Attributes	Scenario 1	Scenario 2	Scenario 3
ECOG-PS	Grade 0-2	Grade 0-2	Grade 0-2
Thrombotic risk	Low	Low	Low
Bleeding risk	Low	Low	Low
Antithrombotic medication	DOAC or VKA	LMWH (therapeutic)	Antiplatelet agent

15.4 Survey: Questions on actual case decisions

In the following (multiple choice) questions, you will be asked to describe one to three actual cases of patients with active cancer, who were considered to receive end-of-life care, in which you considered deprescription of antithrombotic medication.

1. Please select the age category of the patient (*< 40 years; 40-75 years; 75 years or older*)
2. Please indicate the type of antithrombotic medication involved (*DOAC; VKA; LMWH (therapeutic); antiplatelet agent*)
3. Please select the indication of the antithrombotic medication (*atrial fibrillation; treatment of acute VTE-event, prevention of (recurrent) VTE; mechanical heart valves; other indication (free text)*)
4. Please indicate the patient's performance status (*ECOG-PS grade 0-2, ECOG-PS ≥ 3*)
5. Please indicate the estimated prognosis of the patient at the time of consideration (*< 6 months; < 3 months; < 2 weeks*)
6. Please specify the setting of the patient at the time of consideration (*at home without palliative care; at home with palliative care; at rehabilitation facility; at nursing facility; at hospice facility; in 'acute care' setting; other (free text)*).
7. Please select one or more of the attributes that played a role in your consideration of deprescribing the antithrombotic medication; multiple answers are possible (*type of antithrombotic medication; indication of the antithrombotic medication; bleeding risk; thrombotic risk; sex; age; patient's performance status; patient's preference; other (free text)*).
8. Did you decide to deprescribe the antithrombotic treatment? (*yes; no*)

9. If no:

Which of the following attributes made you decide not to deprescribe the antithrombotic drugs? Multiple choices are possible.

Experience with deprescribing: not enough; enough

Symptom burden: high

Burden of medication (administration): low

Thrombotic risk: high

Bleeding risk: low

Antithrombotic medication indication: atrial fibrillation; acute VTE-event, prevention of (recurrent) VTE; mechanical heart valves; other indication (free text)

Sex: male; female, other (selection to be made)

Age: (< 40 years; 40-64 years; 65-74 years; 75 years or older)

Patient's performance status: ECOG-PS 0-2

Patient's prognosis: < 2 weeks; < 3 months; < 6 months (selection to be made)

Patient's preference: continue antithrombotic treatment

Other (free text)

10. If yes:

Which of the following attributes made you decide to deprescribe the antithrombotic drugs?

Multiple choices are possible.

Experience with deprescribing: enough

Symptom burden: low

Burden of medication (administration): high

Thrombotic risk: low

Bleeding risk: high

Antithrombotic medication indication: atrial fibrillation; acute VTE-event, prevention of (recurrent) VTE; mechanical heart valves; other indication (free text)

Sex: male; female, other (selection to be made)

Age: (< 40 years; 40-64 years; 65-74 years; 75 years or older)

Patient's performance status: ECOG-PS grade ≥ 3

Patient's prognosis: < 2 weeks; < 3 months; < 6 months (selection to be made)

Patient's preference: stop antithrombotic treatment

Other (free text)

Tumour-specific

11. Please select the type of cancer (*breast; lung; upper gastro-intestinal (GI); lower GI; endocrine; genito-urinary tract; brain; haematological; skin (excluding squamous/basal cell carcinoma); combination (select more than one); other (free text)*)
12. Please select the stage of cancer (*localized; regional; distant metastasis; not applicable*)
13. Please select the cancer treatment at the time of consideration/decision – multiple options possible (*none; surgery (in the previous 3 months); radiation therapy (in the previous month); chemotherapy (in the previous month); immunotherapy (in the previous month)*)
14. Please select the line of cancer treatment (*first-line, second-line, third-line, fourth-line, not applicable*)

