7. COUNTRIES INVOLVED

The survey will be conducted among healthcare professionals mainly from the eight European countries represented in the SERENITY consortium:

- Denmark
- France
- Germany
- Italy
- The Netherlands
- Poland
- Spain
- United Kingdom

Due to promotion of the project via international networks and social media (s. section 10), we also expect participants from other countries and regions. Depending on the number or proportion of participants from outside Europe, these will be evaluated separately.

8. (TARGETED) NUMBER OF SUBJECTS

The study aims to generate data from a total of at least 800 healthcare professionals (i.e., either 100 each from the countries listed in section 7 or corresponding participant numbers from additional countries) and up to 2400 anonymised patients, considering that each healthcare professional will be asked to describe actual decisions and anonymous data obtained from medical charts in one to three consecutive patients meeting the definitions below at the time of consideration.

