10. DESCRIPTION OF STUDY PROCEDURES

The study will be divided into three phases: the recruitment phase, the FMR-phase and the data analysis phase.

In the **recruitment phase**, the national coordinators of the project group will advertise the study through traditional professional networks as well as their social media channels. Information about the study will be distributed via personal communication, relevant scientific organisations and journals, and via social media. The healthcare professionals of interest will be invited to pre-register for study participation so they can be assigned a unique link to the electronic case report forms (eCRF). During the preregistration, characteristics of the pre-registrants will be checked (i.e., sex, age, profession, years of experience, the country where they are practicing, and the number of cancer patients in palliative care whom they care for on a yearly basis).

In the **FMR phase**, all preregistered participants will be asked simultaneously to complete the survey using the *Castor electronic data capture platform* within seven days.

The survey will be divided into the following sections:

- a) **General questions** regarding end-of-life care (e.g., "When do you consider a patient in end-of-life care?") and (de)prescription of antithrombotic medication to cancer patients during end-of-life care (e.g., "Have you ever considered deprescribing antithrombotic medicine?").
- b) A sequence of **choice scenarios** i.e., hypothetical scenarios that vary with regard to several characteristics (**attributes**; e.g., bleeding risk, thrombotic risk). Attributes will be further specified by varying choice levels (**attribute levels**; e.g., low or high bleeding risk), which are considered relevant for the decision on continuation or stopping antithrombotic medication in the patient population studied. In accordance with the discrete choice experiment (DCE) methodology, participants will be asked to select the healthcare intervention (i.e., either continuation or discontinuation of the antithrombotic therapy) that in their opinion would benefit the patient the most within each choice set.
- c) Participants will be asked to share **actual case decisions** they made in a maximum of three consecutive cases involving patients with active cancer, who were considered to receive end-of-life care. Fully anonymised data of the patients (sex, age category, primary tumour, tumour

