stage, time point in the course of the disease when the conversation about discontinuation of ATT took place, type and indication of ATT) will be collected via multiple-choice questions.

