12. STUDY DURATION AND TIMELINES

The total duration of this study is expected to be twelve months.

The recruitment phase, in which the healthcare professionals will be asked to preregister for study participation, will start in March 2023. One week before the study is open for data entry, preregistered healthcare professionals will receive an email with details on the study launch. Data collection (i.e., the FMR phase) will start in the first week of May 2023 and take seven days. Data analysis and publication of results will be conducted from June to October 2023.

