13. STATISTICAL ANALYSIS

The main analysis of the FMR will be descriptive. Results will be presented for all predefined subgroups and with corresponding 95% confidence intervals. Responses to the DCE will be used to generate preference coefficients for each level of each attribute using random parameters logit regressions, where preference weights represent the relative contribution of the attribute level to the value that participants assigned to an alternative management decision.

The attribute-level coefficients will be expressed as mean preference weights and standard deviations of the mean preference weights, each with appropriate 95% confidence interval. The relative importance of each attribute will be expressed using the within-attribute difference in preference weights as a percentage of the total difference in preference weights across all attributes. For the coefficients, the algebraic sign (positive or negative) of a coefficient reflects whether respondents feel positive or negative with regard to deprescribing. The value of a coefficient indicates the relative importance of the corresponding attribute. The statistical significance of a coefficient ($p \leq 0.05$) indicates that the respondents underline the importance of the attribute within the options in the DCE.

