15.2 Survey: General questions

1. When do you consider a patient in end-of-life care? If the life expectancy is:
A. < 1 year B. < 6 months C. < 3 months D. < 2 weeks
2. When a patient is considered to be in end-of-life care, I **XXX** prescribe antithrombotic medication upon the diagnosis of a thrombotic complication.
A. never B. sometimes C. often D. always
3. Have you ever deprescribed (i.e., terminated) antithrombotic medication in end-of-life care of cancer patients?
A. no B yes

In case of no, the participant will not be redirected to certain questions.

4. When a patient is considered to be in end-of-life care, I **XXX** deprescribe antithrombotic medication.
A. never B. sometimes C. often D. always
5. Give an estimate of the frequency per year that you consider deprescribing antithrombotic medication in patients, considered to be in end-of-life care:
XXX /year
6. Give an estimate of the frequency per year that you actually deprescribed antithrombotic medication in patients considered to be in end-of-life care:

XXX /year

7. Do you discuss deprescription of antithrombotic medication in patients at the end of life with colleagues?
A. never B. sometimes C. frequently D. always
8. Please indicate what factors determine whether you prescribe antithrombotic medication in patients considered to be in end-of-life care.
9. Please indicate what factors determine whether you deprescribe antithrombotic medication in patients considered to be in end-of-life care.

15.2.1 Examples of factors relevant to questions 8 and 9

1. Antithrombotic medication:
 - DOAC or VKA
 - LMWH (therapeutic)
 - Antiplatelet agent
2. Indication for antithrombotic medication:
 - Atrial fibrillation
 - Treatment of acute VTE event or prevention of (recurrent) VTE
 - Mechanical heart valves
 - Other indication
3. Bleeding risk:
 - Low
 - High
4. Thrombotic risk:
 - Low
 - High
5. Sex:
 - Female
 - Male
 - Other
6. Age:
 - < 40 years
 - 40-75 years
 - > 75 years
7. Patient's performance status:
 - Eastern Clinical Oncology Group performance status (ECOG-PS) grade 0-2
[Oken MM et al. Am J Clin Oncol. 1982]
 - ECOG-PS grade ≥ 3
8. Patient prognosis:
 - < 6 months
 - < 3 months
 - < 2 weeks

9. Patient preference:

- Stop antithrombotic treatment
- Continue antithrombotic treatment

10. Other

Free text

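### The drafted case form (15.4) does not pass on the consecutive-case rule of sections 8 and 10c, and no start point is given, so respondents can choose which cases to report

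*Combined protocol and SAP*

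**What the plan says.** The selection rule appears twice in the body of the protocol. Section 8 expects data "in one to three consecutive patients meeting the definitions below at the time of consideration", drawn from medical charts. Section 10c asks for decisions "they made in a maximum of three consecutive cases involving patients with active cancer, who were considered to receive end-of-life care".

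The only drafted wording addressed to the respondent is the lead-in to 15.4: "you will be asked to describe one to three actual cases of patients with active cancer, who were considered to receive end-of-life care". It adds that deprescription was considered in those cases, but does not say that they must be consecutive.

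Section 12 gives the timing of the survey: "Data collection (i.e., the FMR phase) will start in the first week of May 2023 and take seven days". Section 10 describes the same seven days as the time allowed to complete it. For time at case level, section 10c lists the "time point in the course of the disease when the conversation about discontinuation of ATT took place", which is a stage of illness and not a calendar date.

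On analysis, section 13 says: "The main analysis of the FMR will be descriptive". Results are to carry 95% confidence intervals. No handling of case selection is described.

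**The concern.** Taking consecutive cases is the plan's own protection against respondents reporting memorable or favourable ones. It works only if the respondent is told of it and knows where the run begins. The form as drafted does neither: any one to three cases would satisfy it. Even with the word added, any three adjacent cases would qualify unless a start point is named.

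The case series is the only patient-level record of actual decisions, and it serves the first objective, describing European practice. If cases are picked according to what was decided, the Q8 share moves. So do the pooled answers to Q7, if the factors considered differ between stopped and continued cases. The loss cannot be repaired after data entry, because none of the 14 items in 15.4 records a case date, the order of cases or the number of eligible cases.

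**Working it through.** **Text comparison.**

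| Place | Consecutive? | Direction | Start point |
|---|---|---|---|
| Section 8 | yes | backward, implied by use of charts | none |
| Section 10c | yes | backward, implied by past tense | none |
| 15.4 lead-in | no | backward, implied by past tense | none |

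Section 8's phrase about the time of consideration fixes when eligibility is judged, not which case comes first.

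**The plan's own figure.** 8 countries × 100 = 800 respondents, and 800 × 3 = 2400 cases, as section 8 states. Which cases are reported does not affect this ceiling.

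**Illustration of size.** The documents give none of these inputs; all are assumptions:
- r = 0.60, the true share of eligible cases in which treatment was stopped;
- w = 2 or 0.5, the weight of a stopped case relative to a continued one when the respondent picks;
- n, the number of eligible cases per respondent, of which three are reported.

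Method: the number stopped among n is Binomial(n, r). Three cases are drawn one at a time without replacement. With s stopped and c continued cases left, the chance that the next one drawn is a stopped case is ws/(ws + c). The expected share stopped among the three is averaged over the binomial distribution.

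| n | Q8 share, w = 2 | Q8 share, w = 0.5 |
|---|---|---|
| 3 (all reported) | 60.0% | 60.0% |
| 4 | 65.8% | 54.5% |
| 6 | 69.9% | 49.9% |
| 12 | 72.8% | 46.0% |
| 24 | 74.0% | 44.4% |

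The large-pool limit is wr/(wr + 1 − r): 1.2/1.6 = 75.0% and 0.3/0.7 = 42.9%. With a milder preference (w = 1.5 or 1/1.5) and n = 12, the shares are 67.7% and 51.9%.

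A small pool is safe only if every case is reported. With one case reported out of two, Q8 shows 0.36 + 0.48 × 2/3 = 68% for w = 2, or 0.36 + 0.48 × 1/3 = 52% for w = 0.5.

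**Sensitivity to a common stop rate.** The table assumes that every respondent stops 60% of cases. Respondents who always or never stop cannot bias Q8 by picking, so variation between respondents shrinks the effect. Replacing the binomial with a beta-binomial of mean 0.60, at n = 12:

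| Intra-respondent correlation | w = 2 | w = 0.5 |
|---|---|---|
| 0 | 72.8% | 46.0% |
| 0.3 | 69.2% | 50.4% |
| 0.5 | 66.6% | 53.2% |

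At 0.5 the shift is about half as large: 66.6 − 60 = 6.6 points upward against 12.8.

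**Would the interval show it?** At 2400 cases and 60%, the simple 95% half-width is 1.96 × √(0.6 × 0.4/2400) = 2.0 points, ignoring clustering. It reflects sampling error only and would not reveal a selection shift.

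**The case against.** The strongest reply is that the protocol already commits, twice, to asking for consecutive cases, and that 15.4 is visibly not the final form. It has no separate item for the patient's sex, nor one for the time point of the conversation, both of which section 10c promises. The released form may well carry the instruction. That is fair, and it limits the point to the supplied text. It does not remove it: the drafted wording lacks the rule, and no section gives a start point that a final form could take over.

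The counting direction is also largely settled. A reader might infer from the seven-day collection period that cases could equally be counted forward within that week. The documents do not support this. The seven days are for completing the survey, and the past tense and the reference to charts point backward. Only the anchor is missing.

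A reader might also infer that the reasons given in Q9 and Q10 would be distorted. Those items are asked separately of continued and stopped cases. If cases are picked by decision alone and respondents share one stop rate, picking changes how many cases reach each branch, not the mix of reasons within it. A shift there would need picking on the reasons themselves, for which the documents give no basis.

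Finally, the analysis is descriptive, and no section names the Q8 share as an endpoint. That lowers the weight of the point, but Q8 still records what was actually decided.

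**Conclusion.** The point holds as a mismatch between the stated sampling rule and the drafted instruction, together with a missing start point and no means of checking afterwards. This rests on the text alone and is firm.

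The consequence is not firm. Whether respondents would pick cases, how strongly and in which direction is unknown. It would be tempting to conclude that the deprescribing share will be overstated; nothing in the documents supports either direction. The illustrated range at 12 eligible cases, 73% or 46% under one common stop rate and about 67% or 53% at an intra-respondent correlation of 0.5, rests wholly on assumed values for r, w, n and the correlation. The bias is nil where all eligible cases are reported.

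It is worth correcting before launch, because the change is small and the omission cannot be made good later.

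**What to change.** 1. Reword the 15.4 lead-in, for example: *Please describe your most recent consecutive patients (up to three; if you have had three or more, please report three) with active cancer in end-of-life care in whom you considered deprescribing antithrombotic medication, counting back from the day you complete this survey, whatever you decided.* Asking for three where three exist also removes most of the choice of how many to report.
2. Use the same entry criterion in sections 8 and 10c, including that deprescription was considered, which they now only imply.
3. Add a sentence to section 13 saying that the Q8 share is conditional on deprescription having been considered.

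The cost is a few sentences. No data item is added, the separate export of the case section is untouched, and the ceiling of 2400 cases stays. Respondents must look up their latest cases, a small burden that section 8 already expects by referring to charts. Adherence would still not be verifiable from the data, since no date or order is recorded, but the respondent would at least be told the rule.

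### The case-level age bands in 15.4 question 1 overlap at age 75 and do not match the bands used for decision reasons in questions 9 and 10

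*Combined protocol and SAP*

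**What the plan says.** Patient age is banded in three places in the appendices, each time differently.

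- Section 15.4 question 1 asks the age group of each reported case, with an under-40 option followed by "40-75 years; 75 years or older".
- Section 15.4 questions 9 and 10 ask what led the respondent to continue or to stop. Age is one of the listed attributes, with bands "< 40 years; 40-64 years; 65-74 years; 75 years or older" in both questions.
- Section 15.2.1 item 6, among the example factors for the general questions, uses under 40, 40 to 75, and strictly above 75.

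Questions 9 and 10 are multi-select lists of reasons. Question 9 reads: "Which of the following attributes made you decide not to deprescribe the antithrombotic drugs? Multiple choices are possible". Section 10 gives the patient items to be collected, starting "Fully anonymised data of the patients (sex, age category, primary tumour, tumour"; age appears there as a category, and no exact-age field appears anywhere. Section 13 makes the main analysis of the flash mob part descriptive: "Results will be presented for all predefined subgroups and with corresponding 95% confidence intervals". No section gives a rule for a patient aged exactly 75 or a mapping between the three sets of bands.

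**The concern.** In a descriptive survey the answer options fix what can be reported. Age has two roles here: it describes each case (15.4 question 1), and it is a possible reason for the decision (15.4 questions 7, 9 and 10).

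Two things go wrong. First, the question 1 options are not mutually exclusive, so two respondents with identical 75-year-old patients can validly give different answers. Second, the finer bands in questions 9 and 10 are recorded only where the respondent cites age as a reason. They can supply a numerator, such as the number of 65-74-year-olds in whom age counted, but the number of all reported cases aged 65-74 is never collected.

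At stake are the age tabulations of the actual case decisions: how often treatment was stopped, and how often age was cited, by age band. With no exact age on file, the bands cannot be redrawn later.

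**Working it through.** The plan gives no figure to reproduce; the check is on band boundaries.

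**Step 1: overlaps and gaps.** Each set of bands was written as whole-year intervals, and for every age from 18 to 110 the number of bands containing it was counted.

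| Place | Bands | Ages in two bands | Ages in no band | Where 75 falls |
|---|---|---|---|---|
| 15.2.1 item 6 | <40; 40-75; >75 | none | none | middle |
| 15.4 question 1 | <40; 40-75; ≥75 | 75 | none | middle and top |
| 15.4 questions 9 and 10 | <40; 40-64; 65-74; ≥75 | none | none | top |

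The only overlap is at age 75, and only in question 1. Under 40 is the only band that is the same, and cleanly separated, in all three places.

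**Step 2: denominators.** A reason band has a case-level denominator only if it can be built from whole question 1 bands.

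- <40: equals a question 1 band. Denominator available.
- 40-64: lies strictly inside 40-75. No denominator.
- 65-74: lies strictly inside 40-75. No denominator.
- ≥75: has a question 1 counterpart, but some 75-year-olds may have been entered under 40-75. Denominator blurred.

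**Step 3: size of the overlap.** The documents give no age distribution. Assume that 3-4% of cases are aged exactly 75. The maximum number of cases is 2400 (section 8).

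- 0.03 × 2400 = 72
- 0.04 × 2400 = 96

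These are cases with two valid answers, not cases misplaced. If one answer is given per case, the number placed differently from the question 9 and 10 convention is some fraction of 72-96, and smaller again if fewer than 2400 cases are reported.

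**Step 4: effect of a correction.**

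- Question 1 as <40; 40-74; ≥75: age 75 falls in one band. Merging 40-64 and 65-74 gives 40-74, so questions 9 and 10 collapse exactly onto question 1.
- Question 1 as <40; 40-64; 65-74; ≥75: age 75 falls in one band, and each reason band has its own denominator.

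Neither correction changes a sample size or power figure.

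**The case against.** The strongest reply is that little of value is lost, and much of it stands.

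- A reader might infer that everyone in the middle band has no usable age contrast. If 60-75% of cases were aged 40-74 (an assumption), that would be 0.60 × 2400 = 1440 to 0.75 × 2400 = 1800 cases. The documents do not support this. Those cases can still be compared with under 40 and with the top band. Question 1 can also be cross-tabulated with question 7 (whether age played a role) and question 8 (whether treatment was stopped). Only the split within the middle band is unavailable.
- A reader might also infer that the three parts of the survey cannot be compared on age at all. They can: merging 40-64 with 65-74 brings questions 9 and 10 into line with the other two everywhere except at age 75.
- Section 13 refers to predefined subgroups, but no section names patient age, or a 65-74 group, as one. A named planned analysis is therefore not shown to fail.
- Section 15.2.1 is a list of examples for questions about general practice and does not classify patients. Its mismatch at 75 matters little by itself.
- Age does not appear in the example choice scenarios in 15.3, so the choice model is untouched.
- A coarse band in question 1 fits section 11, which commits to patient data too coarse to identify anyone.

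What the reply does not remove is the overlap itself, or the fact that the plan bands age more finely among the reasons than in the item that would supply the denominator.

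**Conclusion.** The point holds in limited form. Question 1 of section 15.4 has two answers for a patient aged exactly 75. Its bands do not match those in questions 9 and 10, nor, at age 75, the examples in 15.2.1. Because only a category is recorded, 75-year-olds will be classified inconsistently, and reasons recorded for ages 40-64 and 65-74 cannot be turned into proportions of all cases of those ages.

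The effect is confined to descriptive age tabulations of the reported cases. The overlap blurs one year of age, and the figure of 72-96 cases depends wholly on the assumed 3-4% and on reaching the maximum of 2400. The missing denominators matter only if the sponsor wants to report 40-64 separately from 65-74; the bands in questions 9 and 10 suggest some interest in that, but no analysis is stated. The denominator point also assumes that the age band in those questions is filled in only when age is cited, which is how a multi-select list of reasons reads.

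This is a small data-capture error that cannot be undone once the seven-day collection has run, so it should be corrected before launch.

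**What to change.** Choose one of two edits before the survey opens.

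1. **Minimum.** In 15.4 question 1, end the middle band at 74, giving under 40; 40-74; 75 or older. Use the same three bands in 15.2.1 item 6. Questions 9 and 10 can stay as they are, because their bands then collapse exactly onto question 1. The cost is two edited answer lists, and no finer patient data are collected. The 40-64 and 65-74 reason bands would still lack separate denominators and should be reported merged whenever a proportion of cases is given.
2. **If the split at 65 is wanted.** Use under 40; 40-64; 65-74; 75 or older in question 1 and in 15.2.1. In questions 9 and 10, reduce age to a simple tick, with the band taken from question 1. This gives every reason band a denominator. The cost is one extra age split recorded for every case, where at present it is recorded only when age is cited. The sponsor should confirm that this is compatible with the coarsening commitment in section 11, which also rests the absence of an ethics submission partly on no personal patient data being recorded.

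Neither option changes recruitment, the choice model or the sample size.
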